8 EFFICACY EVALUATIONS

8.1 Common Wart Evaluations

In cohort 1 and 2, the largest common wart located on hands, feet (excluding soles), limbs and/or trunk will be selected as the primary injected wart.

In cohort 3, the largest common wart per anatomical region (left or right; arm, hand, leg, foot (excluding sole) or the torso) will be selected as the primary injected wart for a maximum of four warts. For cohort 3, each injected wart must be located on a different anatomical region. Flat, plantar, facial, periungual, or genital warts or warts in region of pre-existing inflammatory condition are excluded.

8.1.1 Common wart measurement

The visually largest six common warts (including the primary injectable wart(s)) that can be readily identified will be measured at Baseline Visit (V3) and during the study (referred as "measured warts"). Unless the wart location can be easily identified in writing using anatomical terms, these (up to 6) largest common injectable warts will be mapped on transparencies or drawn in the medical chart to ensure it is accurately found at every visit. The mapping process on transparencies will be described in the Study Manual.

Each measured wart will be documented in the source document and reported on the eCRF, with its size, age, treatment history and location. Size will be determined by measuring in mm the longest and orthogonal diameters of the wart using a ruler.

8.1.2 Evaluation of primary injected wart status

The size and status (resolved, partially resolved, or no response) of each primary injected wart will be documented at each visit. Complete resolution of a wart is the absence of visual or measurable presence

Nielsen- CFW-2D Page 36 of 54

of verruca vulgaris. Complete resolution of all common warts is the absence of any common warts (i.e. wart count = 0).

8.1.3 Evaluation of presence or absence of common warts other than the measured common warts

New warts (those not noted at Baseline Visit (V3)) can be recorded in Progress Notes at any given visit, but are not tracked except as noted in **Section 8.1.4**. If the investigator notes an occurrence of new warts that is considered clinically abnormal or unusual, note as an Adverse Event.

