The primary endpoint is the number and proportion of subjects with complete resolution of the primary injected wart(s). The proportion of subjects with the complete resolution of treated warts will be compared among all treatment groups using the Cochran-Mantel-Haenszel test with a stratification factor of single versus multiple anatomical regions. In addition each active treatment will be compared with the pooled placebo in a similar manner. There will be no adjustment of the type 1 error for multiple comparisons.

Sample Size Determination

A total of approximately 156 subjects will be enrolled into the study with approximately 52 subjects in each active treatment arm and the pooled placebo group. One assumes that the pooled placebo arm has a 24% complete resolution rate and one of the active treatment arms has a complete resolution rate of 70%. The statistical comparison between each active treatment and the pooled placebo will be conducted at the 0.05 significance level. It is assumed that at least 90% of the subjects will either complete the study or reach complete resolution. A sample size of approximately 52 per arm will provide 94% power to detect a statistically significant difference between an active treatment and the pooled placebo. The assumed Nielsen- CFW-2D

Protocol Final version 5.0: 06Dec2016

Nielsen- CFW-2D Protocol Final version 5.0: 06Dec2016

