4 STUDY ENDPOINTS

4.1 Primary Efficacy Endpoint

The primary efficacy endpoint is the number and proportion of subjects with the primary injected wart(s) completely resolved at any treatment or Follow-up visit.

[figure not shown]
In Cohort 1 and 2, the largest common wart located on hands, feet (excluding soles), limbs, and/or trunk will be selected as the primary injected wart. In Cohort 3, the largest common wart per anatomical region (left or right; arm, hand, leg, foot (excluding sole) or the torso) will be selected as the primary injected warts for a minimum of 2 and a maximum of 4 warts. In Cohort 3 subjects, injected warts must be in different anatomical regions. Warts in flat, plantar, facial, periungual, or genital or in a region of pre-existing inflammatory condition are excluded from injection.

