7.1.1 Hypothesis Testing

All inferential hypothesis tests will be two-sided at $\alpha = 0.05$ significance level. There will be no adjustment of Type I error for multiple comparisons due to exploratory nature of this early phase study.

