7.2 Efficacy Analyses

7.2.1 Analyses of Primary Endpoint

If the area of a measured wart at baseline becomes 0 at a post-baseline evaluation visit, the wart will be considered as completely resolved. For each of the four treatment groups, the number and percent of subjects achieving complete resolution of the primary injected wart(s) will be calculated and summarized.

[figure not shown]

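### The readable SAP rule scores resolution from area = 0 and does not use the investigator's recorded status, so a visit where the two disagree could count as a success that the protocol's definition does not allow

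*Protocol*

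**What the plan says.** Protocol 8.1.2 defines the outcome: "Complete resolution of a wart is the absence of visual or measurable presence" (the sentence continues over a page break and names the wart type). The same section requires two records: "The size and status (resolved, partially resolved, or no response) of each primary injected wart will be documented at each visit". The visit schedules in Protocol Appendix A and SAP Table 1 list the status evaluation on its own row, separate from measurement, at V4 to V15.

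Protocol 8.1.1 says how size is obtained: "Size will be determined by measuring in mm the longest and orthogonal diameters of the wart using a ruler". The readable text gives no smallest recordable size, no rounding rule and no formula turning two diameters into an area.

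SAP 7.2.1 gives the scoring rule: "If the area of a measured wart at baseline becomes 0 at a post-baseline evaluation visit, the wart will be considered as completely resolved". Its readable part does not mention the status and does not say what happens if status and area disagree.

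SAP 4.1 counts subjects "with the primary injected wart(s) completely resolved at any treatment or Follow-up visit". The same section gives Cohort 3 subjects two to four primary warts; Cohorts 1 and 2 have one.

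**The concern.** The protocol collects a dedicated judgement of whether the primary wart has gone, and the readable analysis rule does not use it. If a wart is entered with area 0 while its status is partially resolved or no response, the SAP calls it resolved and the protocol does not.

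Two features of the design make this worth settling. First, success at any visit suffices and the readable text asks for no confirmation at a later visit, so a single discordant entry can fix a subject's outcome in Cohorts 1 and 2. Second, under Protocol 6.1 the investigator moves on to another wart only after the primary wart shows a complete response. The analysis could therefore score a wart as resolved while the investigator still judges it present and goes on injecting it. If the choice of governing variable is left until after unblinding, it becomes a post hoc decision about the primary endpoint.

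**Working it through.** **1. The two rules side by side.** The protocol's standard is met only when the wart is neither visible nor measurable. The SAP's readable rule tests the measurable part alone. For one primary wart at one visit:

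| Status recorded | Area recorded | SAP 7.2.1 as readable | Protocol 8.1.2 |
|---|---|---|---|
| resolved | 0 | resolved | resolved |
| not resolved | 0 | resolved | not resolved |
| resolved | above 0 | not resolved | not resolved (still measurable) |
| not resolved | above 0 | not resolved | not resolved |

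The rules part only in the second row. There the SAP can only add responders relative to the protocol.

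**2. How the second row could arise.** A very small remnant might be rounded to 0 mm. If area is a product of the two diameters (an assumption, since no formula is readable), one diameter entered as 0 would be enough. The documents neither describe nor exclude either route.

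**3. Size.** The plan states no figure for disagreement, so there is none to reproduce. The Protocol's planning rates are the only efficacy rates available: "One assumes that the pooled placebo arm has a 24% complete resolution rate", against 70% in an active arm, a difference of 46 points. The stated 94% power plays no part in this point. At 24% against 70%, a pooled-variance normal approximation gives 99.9% with 52 per arm and 99.1% with the 39 against 39 implied by the cohort sizes. The sample-size paragraph is cut off, so that gap is a separate matter.

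An illustration for a subject with one primary wart follows. Assume a false-zero probability f per visit, independent across the 12 visits V4 to V15, with all visits attended and the same f in both arms. The share of true non-responders ever scored as resolved is g = 1 − (1 − f)^12, and an observed rate is p + (1 − p)g. Differences are taken before rounding.

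| f (assumed) | g | 24% becomes | 70% becomes | Difference, points |
|---|---|---|---|---|
| 0.5% | 5.8% | 28.4% | 71.8% | 43.3 |
| 1% | 11.4% | 32.6% | 73.4% | 40.8 |
| 2% | 21.5% | 40.4% | 76.5% | 36.1 |

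**4. Where the illustration fails.** With two primary warts in Cohort 3, f = 1% and independence, both are falsely zero at some visit with probability 0.114² ≈ 1.3%. If the zeros must fall at the same visit, it is 1 − (1 − 0.01²)^12 ≈ 0.1%. Cohort 3 also supplies 13 of the 39 pooled placebo subjects, so the table does not describe the pooled comparison.

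**5. Direction.** Equal error in both arms dilutes the difference, as in the table. Unequal error could do the opposite. Take the levels stated in the documents ("The statistical comparison between each active treatment and the pooled placebo will be conducted at the 0.05 significance level" and "All inferential hypothesis tests will be two-sided at" 0.05), 39 against 39, and a true rate of 24% in both arms. If 5% of unresolved subjects are misscored in the active arm only, its observed rate is 0.24 + 0.05 × 0.76 = 27.8%. The same approximation then gives a 5.7% chance of a significant result favouring active, against a nominal 2.5%. Nothing in the documents says which pattern is more likely, or that either occurs.

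**The case against.** The strongest reply is that area = 0 is simply how a dataset encodes the protocol's definition. A wart that can be seen normally has a diameter, so a ruler area of 0 and a resolved status should coincide. Warts chosen for injection measure 3 to 20 mm at baseline, and the primary wart is the largest, or the largest in its region. A wart that has not responded is not plausibly read as 0 mm; only near-cleared remnants are at risk. A constant error rate over every non-responder and all 12 visits therefore overstates the problem. All of this stands.

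Text is also missing. A figure not shown follows the rule in SAP 7.2.1 and another sits in SAP 4.1, so the status may be dealt with there. That also stands, and limits the point to what can be read.

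Even on generous assumptions the damage is moderate. If 5%, 10% or 20% of unresolved subjects were misscored equally in both arms, power at 39 against 39 would still be 98.3%, 96.9% or 92.4% by the same approximation.

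A reader might infer that the SAP has knowingly adopted a looser endpoint and that visibly persisting warts will be counted as successes. The documents do not support that: they nowhere allow a visible wart to be entered as 0. What the reply does not remove is the lack of any readable rule for a visit on which the two records disagree.

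**Conclusion.** The point holds as a gap in the scoring rule of the primary endpoint. The protocol has a two-part definition and a recorded status; the readable SAP rule uses area only. A visit with area 0 and a status other than resolved would be scored as resolution against the protocol's definition. One such visit decides the outcome in Cohorts 1 and 2, whereas in Cohort 3 every primary wart must be scored resolved.

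The size and direction of any bias are unknown. It is tempting to read the table as a forecast that the 46-point difference will shrink to somewhere between 36 and 43. It is not: the per-visit rates are assumed, independence and full attendance are assumed, and the calculation applies only to subjects with one primary wart. The case for acting rests on the low cost of closing the gap, not on demonstrated harm.

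**What to change.** In SAP 7.2.1, count a primary wart as resolved at a visit only if the recorded status is resolved and the area is 0, with both diameters 0. Before unblinding, list every visit at which status and area disagree and query it with the site. Report the area-only version as a sensitivity analysis, so that a reader can see whether the choice matters.

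The cost is small: a sentence or two in the SAP, one listing, some data queries, and a responder count that may be slightly lower, since the stricter rule can only remove successes. Protocol 8.1.1 states that size goes on the eCRF. That the status is there too is inferred from its being documented at each visit and should be confirmed.

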8.1.4 Presence or absence of common warts in designated anatomical areas

At the Baseline Visit (V3) the presence or absence of common warts in the following anatomical areas will be assessed: left arm, right arm, left hand, right hand, left leg, right leg, left foot (excluding sole), right foot (excluding sole) and torso. The presence or absence of common wart in these anatomical areas will also be assessed at Injection Visit V7, Efficacy Evaluation Visit (V13) and Follow-up Visit (V15).

New common warts in anatomical areas will be defined as the presence of common warts at V7, V13 and/or V15 in anatomical area(s) where **NO common warts in that anatomic area were present at Baseline Visit** (V3). New warts in areas that previously were noted to have warts should not be recorded as such in this examination (see Section 8.13).

[figure not shown]
9 SAFETY EVALUATIONS

Investigators are responsible for monitoring the safety of subjects who are participating in this study and for alerting the Sponsor of any observation that seems unusual, even if this observation may be considered an unanticipated benefit to the subject. The Investigator is responsible for appropriate medical care of subjects during the study.

Safety will be evaluated by collecting AEs and clinically significant changes in safety laboratories or vital signs. The reported AEs will be coded according to Medical Dictionary for Regulatory Activities (MedDRA) terminology.

The number and percentage of subjects with at least one AE will be tabulated. For a given AE, a subject will be counted once even if he or she has experienced multiple episodes for that particular AE. The occurrence of AEs by MedDRA System Organ Class (SOC) and preferred term and the severity and relationship of the AE to the study drug will be summarized using the number and percentage of subjects.

Nielsen- CFW-2D Protocol Final version 5.0: 06Dec2016

Study participants will be instructed to contact the Investigator immediately in the event they experience any severe sign or symptom, or feel they need to seek medical attention. For this purpose, they will be provided with an emergency number (available 24 hours daily, 7 days weekly) to report the event and/or seek medical advice and assistance.

9.2 Adverse Events

An AE is any untoward medical occurrence in a subject administered a pharmaceutical product, without regard to the possibility of a causal relationship with this treatment. Lack of drug effect is not an AE in clinical trials because the purpose of the clinical trial is to establish drug effect.

Any documented pregnancy will be tracked and followed through outcome. While pregnancy itself is not considered an AE or an SAE, any pregnancy complications or elective termination of a pregnancy for medical reasons will be recorded as an AE and evaluated as a possible SAE.

Prior to enrollment, study site personnel will note the occurrence and nature of each subject's medical condition(s) in the appropriate section of the source document and eCRF. During the study, site personnel will again note any change in the pre-existing condition(s) and the occurrence and nature of any AEs.

CANDIN will be administered in accordance with the US labeled indication for assessment of the subject's DTH response to Candida antigen. AE collection will begin at the time of the DTH injection (Screening Visit 1).

CANDIN administered intralesionally is the investigational product in this study. Treatment-Emergent AEs (TEAEs) will be those arising after the first intralesional wart(s) injection.

If a subject experiences an AE after the informed consent document is signed, but before CANDIN is Nielsen- CFW-2D Page 38 of 54

Protocol Final version 5.0: 06Dec2016

administered for assessment of the DTH response, the event will be recorded as a non-treatment emergent AE in the source document. If the subject is randomized, the non-treatment emergent event will also be captured in the eCRF. If the subject screen fails, the event will not be captured in the eCRF or in the clinical database.

AEs reported as related to CANDIN administered for assessment of the DTH response will be described in the source document and assessed for expectedness and regulatory reportability using the Candin package insert. If the subject is randomized, the AE related to Candin for the DTH assessment will also be captured in the eCRF.

Injection site AEs may be captured from either subject diaries or during Treatment and Follow-up Visits. In all cases, causality and severity of injection site TEAEs are assessed by Investigator as described in Sections 9.2.1 and 9.2.2, respectively.

All unresolved, at least possibly related AEs and SAEs will be followed until resolution or until the Investigator deems the event to be chronic or the event to be stable or until the subject is lost to follow-up.

For subjects randomized to receive study drug, all AEs and SAEs will be described in the source documents and in the eCRF.

Abnormal laboratory values or test results should not be reported as AEs. The criteria for determining whether an abnormal objective test finding should be reported as an AE include the following:

- Test result is associated with accompanying symptoms;
- Test result requires additional diagnostic testing or medical/surgical intervention;
- Test result leads to a change in study dosing or discontinuation from the study, significant additional concomitant drug treatment, or other therapy;
- Test result is considered to be an AE by the Investigator or Sponsor.

Merely repeating an abnormal test, in the absence of any of the above conditions, does not constitute an AE. Any abnormal test result that is determined to be an error does not require reporting as an AE.

9.2.1 Adverse Events Causality

The Investigator will establish causality of the AE to experimental treatment. The Investigator should take into account the subject's history, most recent physical examination findings, and concomitant medications.

The following definitions will be used to determine causality of an AE:

- Not related: temporal relationship of the onset of the AE, relative to the experimental treatment is not reasonable or another cause can explain the occurrence of the AE.
- Unlikely related: temporal relationship of the onset of the AE, relative to the experimental treatment is reasonable; however, an alternative explanation is more likely.
- Possibly related: temporal relationship of the onset of the AE, relative to experimental treatment is reasonable; however, follows no known response pattern to the treatment, and an alternative cause seems more likely or there is sufficient uncertainty about the cause of the event.

Nielsen- CFW-2D Page 39 of 54

- Probably related: temporal relationship of the onset of the AE, relative to the experimental treatment is reasonable, and follows a known response pattern to the treatment, but a potential alternative cause may be present.
- Related: temporal relationship of the onset of the AE, relative to the experimental treatment is reasonable, follows a known response pattern to the treatment, and an alternative cause is unlikely.

9.2.2 Adverse Events Severity

The intensity of an AE is an estimate of the relative severity of the event made by the Investigator based on his or her clinical experience and familiarity with the literature. The severity of AEs at the injection site will be estimated using the table below from the FDA Guidance for Industry: Toxicity Grading Scale for Healthy Adult and Adolescent Volunteers Enrolled in Preventative Vaccine Clinical Trials (see below).²⁰ The following definitions are to be used to rate the severity of AEs that are not at the injection site:

- Mild: The symptom is barely noticeable to the subject and does not influence performance of daily activities. Treatment is not ordinarily indicated.
- Moderate: The symptom is sufficiently severe to make the subject uncomfortable, and performance of daily activities is influenced. Treatment may be necessary.
- Severe: The symptom causes severe discomfort, and daily activities are significantly impaired or prevented. Treatment may be necessary. Note-severe intensity of an AE such as injection site pain does not necessarily mean that it is a SAE (see Section 9.3)

The following definitions from the FDA Guidance for Industry: Toxicity Grading Scale for Healthy Adult and Adolescent Volunteers Enrolled in Preventative Vaccine Clinical Trials will be used to rate the severity of an injection site AE.

Local Reaction to	Mild (Grade 1)	Moderate (Grade 2)	Severe (Grade 3)	Potentially Life
Injection				Threatening (Grade 4)
Pain	Does not interfere with	Repeated use of non-	Any use of narcotic	Emergency room visit or
	activity	narcotic pain reliever	pain reliever by	hospitalization
		>24 h or interferes with	physician or prevents	
		normal daily activity	normal daily activity	
Tenderness	Mild discomfort to	Discomfort with	Significant discomfort	Emergency room visit or
	touch	movement	at rest	hospitalization
Erythema/Redness*	2.5 – 5 cm	5.1—10 cm	>10 cm	Necrosis or severe
				exfoliative dermatitis
Induration/Swelling **	2.5 – 5 cm and does	5.1—10 cm or	>10 cm or prevents	Necrosis
	not interfere with	interferes with normal	normal daily activity	
	normal daily activity	daily activity		

^{*}In addition to grading the measure local reaction at the greatest single diameter, the measurement should be recorded as a continuous variable.

9.3 Serious Adverse Events

If a subject experiences a SAE after the informed consent document is signed, but before CANDIN is administered for assessment of the DTH response, the event will be recorded as a non-treatment emergent SAE in the source document. If the subject is randomized, the non-treatment emergent SAE will also be captured in the source and reported in the CRF. If the subject screen fails, the SAE will not be reported in

Nielsen- CFW-2D Page 40 of 54

^{**}Induration/Swelling should be evaluated and graded using the functional scale as well as the actual measurement.

the eCRF.

CANDIN will be administered in accordance with the US labeled indication for assessment of the subject's DTH response to Candida antigen. SAEs reported as related to Candin administered for the DTH assessment will be described in the source document and assessed for expectedness and regulatory reportability using the Candin package insert. If the subject is randomized, the SAE related to Candin administered for the DTH assessment will also be captured in the eCRF.

All SAEs occurring following wart injections and up to 30 days following the last wart injection will be captured in the source document and reported in the CRF.

A SAE (event/experience) or reaction is any untoward medical occurrence that at any dose:

- results in death,
- is life-threatening,

NOTE: The term "life-threatening" in the definition of "serious" refers to an event in which the subject was at risk of death at the time of the event; it does not refer to an event which hypothetically might have caused death if it were more severe.

- requires in-subject hospitalization or prolongation of existing hospitalization,
- results in persistent or significant disability/incapacity, or
- is a congenital anomaly/birth defect.

Medical and scientific judgment should be exercised in deciding whether expedited reporting is appropriate in other situations, such as important medical events that may not be immediately life-threatening or result in death or hospitalization but may jeopardize the subject or may require intervention to prevent one of the other outcomes listed in the definition above. These should also usually be considered serious.

Examples of such events are intensive treatment in an emergency room or at home for allergic bronchospasm; blood dyscrasias or convulsions that do not result in hospitalization; or development of drug dependency or drug abuse.

9.3.1 SAE Reporting:

Any SAE, related or not, occurring during the study as described above must be reported as soon as possible using the SAE form provided and followed by fax within **24 hours** of awareness to:

For each SAE received, the Sponsor will make a determination as to whether the criteria for expedited reporting to relevant regulatory authorities have been met. The Sponsor will manage the expedited

[figure not shown]
Nielsen- CFW-2D Page 41 of 54

reporting of relevant safety information to concerned health authorities and competent authorities in accordance with local laws and regulations.

The Sponsor will assess the expectedness of each SAE to the study treatment. The current Investigator's Brochure will be used as the reference document to assess expectedness of the event to study drug.

